5.3.3. Caffeine, Alcohol, and Tobacco

- Participants will abstain from caffeine-containing products for 24 hours prior to the start of dosing until collection of the final PK sample of each study period.
- Participants will abstain from alcohol for 24 hours prior to admission to the CRU and continue abstaining from alcohol until collection of the final PK sample of each study period. Participants may undergo an alcohol breath test or blood alcohol test at the discretion of the investigator.
- Participants will not have used tobacco- or nicotine-containing products for 6 months prior to screening and will not use such products during the screening period or after confinement in the CRU.

5.3.4. Activity

- Participants will abstain from strenuous exercise (eg, heavy lifting, weight training, calisthenics, aerobics) for at least 48 hours prior to each blood collection for clinical laboratory tests. Walking at a normal pace will be permitted;
- In order to standardize the conditions on PK sampling days, participants will be required to refrain from lying down (except when required for BP, pulse rate, and ECG measurements), eating, and drinking beverages other than water during the first 4 hours after dosing;
- Participants will be confined to the procedure room for the first 4 hours after dosing on Day 1, except to use the bathroom. After this, participants may be ambulatory but should not engage in strenuous activities.

5.3.5. Photosensitivity

Given the potential for phototoxicity from nonclinical toxicology studies with PF-07284890, participants will be advised to report any reaction to sun exposed skin. In addition, special precautions will be taken to limit any potential photo irritation effect, by minimizing the participants' exposure to light including sunlight, and high intensity UVB light sources such as tanning beds, tanning booths and sunlamps. Participants should be encouraged to apply sunscreen/sunblock daily and to wear clothing that covers areas of exposed skin when outdoors during daylight hours until discharge from the CRU, which is more than 5 half-lives from the last dose of PF-07284890.

5.4. Screen Failures

Screen failures are defined as participants who consent to participate in the clinical study but are not subsequently enrolled in the study. Screen failure data are collected and remain as source and are not reported on the CRF.

Individuals who do not meet the criteria for participation in this study (screen failure) may be rescreened.

6. STUDY INTERVENTION(S) AND CONCOMITANT THERAPY

Study interventions are all prespecified investigational and noninvestigational medicinal products, medical devices, and other interventions (eg, surgical and behavioral) intended to be administered to the study participants during the study conduct.

For the purposes of this protocol, study intervention refers to PF-07284890.

6.1. Study Intervention(s) Administered

Study Intervention(s)	
Intervention Name	PF-07284890
Type	Drug
Dose Formulation	Tablet

PFIZER CONFIDENTIAL

Study Intervention(s)	
Unit Dose Strength(s)	100 mg
Dosage Level(s)	3 single 200-mg doses
Route of Administration	Oral
Use	Experimental
IMP or NIMP/AxMP	IMP
Sourcing	Provided centrally by the sponsor
Packaging and Labeling	Open-label study intervention will be provided in bulk (high-density polyethylene bottle) labeled as required per country requirement.
Current/Former Name(s) or Alias(es)	PF-07284890 ARRY-461 AR00504461

PF-07284890 will be provided by Pfizer as 100 mg tablets for oral administration at the CRU.

Tablets will be supplied to the CRU in bulk along with individual dosing containers for unit dosing.

6.1.1. Administration

Investigational product will be administered orally and according to the conditions described in the [SoA](#) section and Protocol Section [5.3.2 Meals and Dietary Restrictions](#).

For **fasted** period (Sequence 1 Period 1 and Sequence 2 Period 2):

- On Day 1, following an overnight fast of at least 10 hours, the participants will receive 200 mg PF-07284890 (as 2 × 100 mg tablets) administered orally at approximately 08:00 hours (plus or minus 2 hours) without breakfast/standard meal on Day 1.

For **fed** periods (Sequence 2 Period 1 and Sequence 1 Period 2 for the low-fat meal and Period 3 for the high-fat meal):

- On Day 1, following an overnight fast of at least 10 hours, participants will receive breakfast approximately 30 minutes prior to dosing which is to be completed within approximately 20 minutes as outlined in Section [5.3.2 Meals and Dietary Restrictions](#). The participants will then receive 200 mg PF-07284890 (as 2 × 100 mg tablets) administered orally at approximately 08:00 hours (plus or minus 2 hours).

For **all** periods:

- Investigator site personnel will administer study intervention during each period with ambient temperature water to a total volume of approximately 240 mL. Participants will swallow all tablet formulations whole, and will not manipulate or chew the study intervention prior to swallowing.

- In order to standardize the conditions on PK sampling days, all participants will be required to refrain from lying down (except when required for BP, pulse rate, and ECG measurements), eating, and drinking beverages other than water during the first 4 hours after dosing.

6.2. Preparation, Handling, Storage, and Accountability

1. The investigator or designee must confirm that appropriate conditions (eg, temperature) have been maintained during transit for all study interventions received and any discrepancies are reported and resolved before use of the study intervention.
2. Only participants enrolled in the study may receive study intervention and only authorized site staff may supply, prepare, and/or administer study intervention.
3. All study intervention must be stored in a secure, environmentally controlled, and monitored (manual or automated recording) area in accordance with the labeled storage conditions with access limited to the investigator and authorized site staff. At a minimum, daily minimum and maximum temperatures for all site storage locations must be documented and available upon request. Data for nonworking days must indicate the minimum and maximum temperatures since previously documented upon return to business.
4. Any excursions from the study intervention label storage conditions should be reported to Pfizer upon discovery along with actions taken. The site should actively pursue options for returning the study intervention to the labeled storage conditions, as soon as possible. Once an excursion is identified, the study intervention must be quarantined and not used until Pfizer provides permission to use the study intervention. Specific details regarding the excursion definition and information to report for each excursion will be provided to the site in the IPM or PCRU site procedures.
5. Any storage conditions stated in the SRSD will be superseded by the storage conditions stated on the label.
6. Study intervention should be stored in its original container.
7. The investigator, institution, head of the medical institution (where applicable), or authorized site staff is responsible for study intervention accountability, reconciliation, and record maintenance (ie, receipt, reconciliation, and final disposition records), such as the IPAL or sponsor-approved equivalent. All study intervention will be accounted for using a study intervention accountability form/record.
8. Further guidance and information for the final disposition of unused study intervention are provided in the IPM and PCRU's site procedures. All destruction must be adequately documented. If destruction is authorized to take place at the investigator site, the investigator must ensure that the materials are destroyed in

compliance with applicable environmental regulations, institutional policy, and any special instructions provided by Pfizer.

Upon identification of a product complaint, notify the sponsor within 1 business day of discovery as described in the IPM.

6.2.1. Preparation and Dispensing

Within this protocol, preparation refers to the investigator site activities performed to make the study intervention ready for administration or dispensing to the participant by qualified staff. Dispensing is defined as the provision of study intervention, concomitant treatments, and accompanying information by qualified staff member(s) to a healthcare provider or participant in accordance with this protocol. Local health authority regulations or investigator site guidelines may use alternative terms for these activities.

PF-07284890 tablets will be prepared at the CRU in the individual dosing containers by 2 operators, 1 of whom is an appropriately qualified and experienced member of the study staff (eg, physician, nurse, physician's assistant, nurse practitioner, pharmacy assistant/technician, or pharmacist). The tablets will be provided in unit dose containers and labeled in accordance with Pfizer regulations and the clinical site's labeling requirements. See the IPM and/or CRU's site procedures for instructions on how to prepare the study intervention for administration.

6.3. Assignment to Study Intervention

The investigator will assign participant numbers to the participants as they are screened for the study. Pfizer will provide a randomization schedule to the investigator and, in accordance with the randomization numbers, the participant will receive the study treatment regimen assigned to the corresponding randomization number.

6.4. Blinding

This is an open-label study.

6.5. Study Intervention Compliance

When the individual dose for a participant is prepared from a bulk supply, the preparation of the dose will be confirmed by a second qualified member of the study site staff.

Participants will be dosed at the site and receive study intervention directly from the investigator or designee, under medical supervision. The date and time of each dose administered in the clinic will be recorded in the source documents and recorded in the CRF. The dose of study intervention and study participant identification will be confirmed at the time of dosing by a member of the study site staff other than the person administering the study intervention. Study site personnel will examine each participant's mouth to ensure that the study intervention was ingested.

6.6. Dose Modification

No dose modification is anticipated. A 200-mg dose is the maximum dose that will be administered. In case a dose reduction is necessary, the study intervention dose will be reduced or the study will be stopped early.

6.7. Continued Access to Study Intervention After the End of the Study

No study intervention will be provided to participants at the end of their study participation.

6.8. Treatment of Overdose

For this study, any dose of PF-07284890 greater than the prescribed regimen within a 24-hour time period ± 6 hours will be considered an overdose.

Sponsor does not recommend specific treatment for an overdose.

In the event of an overdose, the investigator/treating physician should:

1. Contact the study medical monitor within 24 hours.
2. Closely monitor the participant for any AEs/SAEs and laboratory abnormalities as medically appropriate for at least 5 half-lives or 28 calendar days (whichever is longer) after the overdose of PF-07284890.
3. Document the quantity of the excess dose as well as the duration of the overdose in the CRF.
4. Overdose is reportable to Pfizer Safety **only when associated with an SAE**.
5. Obtain a blood sample for PK analysis within 7 days from the date of the last dose of study intervention if requested by the study medical monitor (determined on a case-by-case basis).

Decisions regarding dose interruptions or modifications will be made by the investigator in consultation with the study medical monitor as needed based on the clinical evaluation of the participant.

6.9. Prior and Concomitant Therapy

Participants will abstain from all concomitant treatments, except for the treatment of adverse events. Use of prescription or nonprescription drugs and dietary and herbal supplements are prohibited within 7 days or 5 half-lives (whichever is longer) prior to the first dose of study intervention. Limited use of nonprescription medications that are not believed to affect participant safety or the overall results of the study may be permitted on a case-by-case basis following approval by the sponsor. Acetaminophen/paracetamol may be used at doses of ≤ 1 g/day.

All concomitant treatments taken during the study must be recorded with indication, daily dose, and start and stop dates of administration. All participants will be questioned about concomitant treatment at each clinic visit.

Treatments taken within 28 days before the first dose of study intervention will be documented as a prior treatment. Treatments taken after the first dose of study intervention will be documented as concomitant treatments.

The following sections contain information on the DDI properties of PF-07284890 and concomitant medications that are prohibited or must be used with caution. These DDI properties are needed for when concomitant medicines must be used to treat AEs. A list of example prohibited medications (eg, strong CYP3A inhibitors and inducers) is provided in Section 10.9, [Appendix 9: Prohibited Concomitant Medications That May Result in DDI](#).

CCI

CYP3A4/5:

Concomitant use of PF-07284890 and a CYP3A4/5 substrate may increase or decrease the exposure of the CYP3A4/5 substrate. Coadministration of PF-07284890 with CYP3A4/5 substrates with narrow therapeutic indices, such as astemizole, terfenadine, cisapride, pimozide, quinidine, tacrolimus, cyclosporine, sirolimus, alfentanil and fentanyl (excluding transdermal patch), or ergot alkaloids (ergotamine, dihydroergotamine)^{16,17} is not permitted. Coadministration with other CYP3A4/5 substrates is permitted but caution is warranted.

CYP2B6:

Concomitant use of PF-07284890 and a CYP2B6 substrate may decrease the exposure of the CYP2B6 substrate. PF-07284890 coadministration with CYP2B6 substrates (eg, a sensitive substrate like bupropion and narrow therapeutic index substrates like efavirenz, also a sensitive substrate, and cyclophosphamide)^{16,17} is permitted but caution is warranted.

CYP2C9:

Concomitant use of PF-07284890 and a CYP2C9 substrate may increase the exposure of the CYP2C9 substrate. CYP2C9 substrates of a narrow therapeutic index, may include warfarin,

phenytoin, glimepiride, glipizide, glyburide, ibuprofen, diclofenac, indomethacin, naproxen, rosiglitazone, sulfamethoxazole, tolbutamide, candesartan, irbesartan, losartan and valsartan.^{16,18} PF-07284890 coadministration with these and other CYP2C9 substrates is permitted but caution is warranted.

BCRP:

Concomitant use of PF-07284890 and a BCRP inhibitor or inducer may alter the rate and/or extent of PF-07284890 absorption, which could potentially increase (inhibitor) or decrease (inducer) PF-07284890 exposures. PF-07284890 coadministration with BCRP inhibitors or inducers is permitted but caution is warranted.

P-glycoprotein:

Concomitant use of PF-07284890 and a P-glycoprotein substrate may increase the exposure of the P-glycoprotein substrate. PF-07284890 coadministration with P-glycoprotein substrates is permitted but caution is warranted.

Acid Reducing Agents:

Concomitant use of PF-07284890 and an acid reducing agent (eg, PPIs) may cause reduced exposures to PF-07284890. PPIs are not allowed within 7 days of study start (C1D1) and during study treatment, but other acid reducing agents (eg, H2 blockers, antacids) may be used, but only between 2 and 3 hours after administration of each dose of PF-07284890.

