2.2.2. Nonclinical Pharmacokinetics and Metabolism

After oral administration, plasma exposures of PF-07284890 (AUC and C_{max}) increased with dose in all species and the absolute oral bioavailability was moderate to complete. GLP TK studies in the rat (doses of 10, 30 and 60 mg/kg) and monkey (doses of 10, 30 and 100 mg/kg) showed less than dose-proportional exposures, as might be expected based on relatively low aqueous solubility (ie, in simulated gastric fluid at 37°C at a pH of 1.2, 131.6 µg/mL, and in fasted state simulated intestinal fluid at a pH of 6.5, 7.6 µg/mL).

In vitro and in vivo metabolite identification suggested that PF-07284890 was metabolized through multiple oxidative and/or glucuronosyltransferase enzymes. Comparisons of across species suggested that direct N-glucuronidation is predicted to be the predominant metabolic route in humans. PF-07284890 glucuronidation is the primary route of metabolism in human hepatocytes with minor contribution from CYP3A4 and aldehyde oxidase. An in vitro study conducted to characterize the involvement of 11 selected human UGTs isoforms in the metabolism of PF-07284890 indicated that UGT2B7 was the principal human isoform likely responsible for primary glucuronide conjugates. Renal clearance was a minor elimination route of unchanged PF-07284890 in rats (<1% of an IV dose) and is predicted to be a minor route across all species, including humans.

Additional information of the nonclinical PK and metabolism of PF-07321332 is available in the current IB.

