2.2.4.2. Summary of PF-07284890 Pharmacokinetics in Human

Single and repeat dose PK data from study C4471001 for monotherapy (Table 4) and for combination therapy when coadministered with binimetinib (Table 5) have been obtained under fasted conditions. PF-07284890 plasma exposure increased in a less than dose proportional manner. For monotherapy, the geometric mean dose-normalized AUC_{24hr} for the 200 mg QD dose was approximately 1.83- and 1.43-fold higher than for the 50-mg dose on C1D1 and C1D15, respectively, when a 4-fold increase would be expected for linear PK. The T_{max} ranged from 1.5 to 6.0 hours across dose groups. The median $t_{1/2}$ across dose groups ranged from 5.7 to 10 hours. PF-07284890 exposures were somewhat higher for combination therapy than for monotherapy, with the difference attributable to PK variability.

The accumulation ratio based on AUC values, R_{AUC} , for patients administered PF-07284890 QD ranged from 0.709 to 1.31, suggesting limited accumulation for QD administration. For BID administration, the limited available data indicate more accumulation occurs, with an R_{AUC} value of 1.69 for the 100 mg BID combination therapy cohort.

Table 4. PF-07284890 Plasma PK Parameters Observed During Monotherapy Dose Escalation in C4471001^a

PF-07284890 Dose and Regimen	Cycle and Day (N)	C_{max} , ng/mL	T_{max} , hr	AUC_{τ} , ng hr/mL	C_{trough} , ng/mL ^b	$t_{1/2}$, hr	R_{Cmax}	R_{AUC}
50 mg QD	C1D1 (2)	795	1.5	8850	—	6.17 ^c	—	—
	C1D15 (2)	1440	1.5	11500	166	10.0	1.79	1.31
100 mg QD	C1D1 (4)	1610 (40.3)	5.0	14400 (40.5)	—	5.83	—	—
	C1D15 (3)	1090 (16.2)	4.0	10400 (8.34)	115 (71.7)	9.11	0.703 (37.1)	0.709 (45.2)

Table 4. PF-07284890 Plasma PK Parameters Observed During Monotherapy Dose Escalation in C4471001^a

PF-07284890 Dose and Regimen	Cycle and Day (N)	C _{max} , ng/mL	T _{max} , hr	AUC _τ , ng hr/mL	C _{trough} , ng/mL ^b	t _½ , hr	R _{Cmax}	R _{AUC}
200 mg QD	C1D1 (3)	1580 (20.3)	6.0	16200 (22.5)	—	5.68	—	—
	C1D15 (3)	1820 (15.5)	2.0	16500 (8.12)	116 (329)	9.64	1.15 (36.6)	1.02 (14.3)
200 mg BID	C1D1 (3)	1890 (39.2)	6.0	17000 ^d	—	—	—	—
	C1D15	ND	ND	ND	ND	ND	ND	ND

- a. Analysis includes bioanalytical data available through 21DEC2021, and results are preliminary data that did not use the actual sample times. Values are Geometric mean (geometric %CV) except for when N <3, for which median values are presented, and for T_{max} and t_½, where median is presented. ND = no data.

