4.3. Justification for Dose

A single 200 mg dose of PF-07284890 is planned for each period of this study.

Following 28 days of once-daily oral administration of PF-07284890 (10, 30 or 60 mg/kg) to Sprague Dawley rats (the sensitive species) in a GLP toxicology study, the STD₁₀ was 60 mg/kg. For the lowest dose of 10 mg/kg, exposures in male and female rats, respectively, are estimated to be 12-32 multiple over those of the planned clinical dose (ie, see details in [Section 2.2.3](#)). The effect of food on PF-07284890 exposures based on its properties (Biopharmaceutics Classification System Class II compound, weak base) is expected to be less than a 2-fold increase;¹² a 2-fold increase in human exposures would reduce these margins to be ~6-16 multiple over those of the planned clinical dose. The clinical data from C4471001 are also important for justifying the 200 mg dose.

Clinical experience with PF-07284890 is based on the FIH study, C4471001, in which dose-finding is being conducted based on the safety and PK of repeat doses of PF-07284890. As of 10 January 2022, the study has dosed 22 patients in the Phase 1a Dose Escalation. At the 4 monotherapy dose levels assessed (50 mg QD, 100 mg QD, 200 mg QD, and 200 mg BID), 12 patients have been treated, 9 patients were DLT evaluable, and no patients experienced DLTs ([Table 2](#)).

Preliminary safety results of the 200 mg QD dose of PF-07284890 in patients resulted in treatment emergent adverse events of Grade 2 worsening gout related to underlying condition and sinus infection/sinusitis as well as Grade 1 anorexia, arthritis, back pain, nausea and pain, all in 1 patient each. With repeat dosing of the 200 mg BID dose schedule, one patient experienced Grade 3 pneumonia, considered not related to study drug. Grade 2 events, occurring in 1 patient each, were ejection fracture decreased considered related to the patient's underlying disease, fatigue, and oxygen saturation decreased preceding diagnosis of

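### Section 6.9 allows H2 blockers and antacids only at 2 to 3 hours after each dose, when absorption may be incomplete, and bars them later, when they could hardly affect that dose

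*Protocol*

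**What the plan says.** The acid-reducer paragraph of Protocol Section 6.9 states that these agents may reduce exposure to PF-07284890. It prohibits proton pump inhibitors from 7 days before study start. Other acid reducers, with H2 blockers and antacids as examples, "may be used, but only between 2 and 3 hours after administration of each dose of PF-07284890". Doses are 5 days apart (Sections 4.1 and 4.3), so read literally the rule permits one hour in about 120.

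The same section limits concomitant treatment to the management of adverse events, plus nonprescription drugs that the sponsor approves case by case. Concomitant treatments must be "recorded with indication, daily dose, and start and stop dates of administration".

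On the drug itself:
- Section 4.3 describes a "Biopharmaceutics Classification System Class II compound, weak base".
- Section 2.2.2 gives a solubility of 131.6 µg/mL in simulated gastric fluid at pH 1.2 and 7.6 µg/mL in fasted-state simulated intestinal fluid at pH 6.5. It says the less than dose-proportional animal exposures "might be expected based on relatively low aqueous solubility".
- Section 2.2.4.2 reports that the human PK data "have been obtained under fasted conditions" and that Tmax "ranged from 1.5 to 6.0 hours across dose groups".
- Table 4 gives a first-dose median Tmax of 6.0 h at 200 mg in both the QD and BID cohorts.

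**The concern.** A rule meant to protect exposure from acid suppression would normally keep these agents away from the absorption phase and allow them once absorption is over. This one does the reverse. A clinician who follows it while treating dyspepsia is directed to an hour that precedes the only first-dose median Tmax values available at the study dose. The same clinician is refused the later hours, when little or no drug is left to absorb.

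The drug is a weak base and is about 17 times less soluble in the pH 6.5 medium (131.6/7.6 = 17.3). The two media differ in more than pH, but an effect of raised gastric pH on undissolved drug is plausible, and the protocol itself states the interaction.

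At stake are the primary endpoints, the within-participant fed/fasted ratios of AUC and Cmax. Compliant use in one period could lower that period's exposure only. In a fed period this lowers the ratio; in the fasted period it raises it, and the fasted period serves both comparisons.

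**Working it through.** **Plan's own figure first.** Section 9.5 gives a 90% CI half-width of ±0.2995 on the log scale for AUC, with 12 evaluable participants and a within-participant SD of 0.3491. The formula is t(0.95, 10) × SD × sqrt(2/12) × sqrt(χ²(0.80, 10)/10) = 1.8125 × 0.3491 × 0.4082 × sqrt(13.442/10) = 0.2995. It reproduces, and is used below as the yardstick.

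**How much drug is left to absorb at 2 to 3 h?** Assumption: a one-compartment model with first-order absorption. Then ke = ln 2 / t½, ka solves Tmax = ln(ka/ke)/(ka − ke), and the unabsorbed share at time t is exp(−ka·t). Inputs are Table 4 medians, except the last row, where a Tmax delayed by food is assumed because all the human data are fasted and two of the three treatments here are fed.

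| Case | Tmax, t½ (h) | ka (/h) | 2 h | 3 h | 12 h | 24 h |
|---|---|---|---|---|---|---|
| 200 mg QD, first dose | 6.0, 5.68 | 0.221 | 64% | 52% | 7% | 0.5% |
| 200 mg QD, Day 15 | 2.0, 9.64 | 1.633 | 4% | 1% | ~0 | ~0 |
| Assumed fed delay | 8.0, 5.68 | 0.128 | – | – | 22% | 5% |

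In both cases taken from Table 4, the permitted hour has more drug left to absorb than the barred hours from 12 h onward. The assumed fed case favours starting at 24 h rather than 12 h.

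**What would one affected participant do?** If a share L of one participant's AUC is lost in one treatment, with 12 participants, the geometric mean ratio moves by (1 − L)^(1/12).
- Day 15 case, all remaining drug lost at 3 h: (1 − 0.0074)^(1/12) = 0.9994. The log shift is 0.0006, or 0.2% of 0.2995.
- Day 15 case, all remaining drug lost at 2 h: (1 − 0.038)^(1/12) = 0.9968, or 1.1% of the half-width.
- Assumed 50% loss: 0.50^(1/12) = 0.944. The log shift is 0.0578, or 19% of the half-width.

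In the slow case a 50% loss needs 0.5/0.643 = 78% (use at 2 h) to 0.5/0.515 = 97% (use at 3 h) of the remaining drug to go unabsorbed. The documents give no interaction size, and losses that complete are unlikely.

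**Cost of excluding one participant.** With 6 and 5 per sequence (9 df), t(0.95, 9) × 0.3491 × sqrt(0.5 × (1/6 + 1/5)) × sqrt(χ²(0.80, 9)/9) = 0.3196, which is 6.7% wider than 0.2995. Exclusion should therefore not be automatic.

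**Spacing of the proposed window.** 120 − 72 = 48 h clear before the next dose. Under the present rule it is 120 − 3 = 117 h.

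**The case against.** The case for leaving the rule alone has real force.

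- **Rare use.** Treatment is limited to adverse events or sponsor-approved nonprescription drugs, and approval already asks whether the drug would affect the results. This stands. It limits the impact, but does not justify the choice of hour.
- **Weak mechanism.** The model gives unabsorbed drug, whereas a pH effect acts on undissolved drug, and the documents do not say how much is undissolved at 2 to 3 h. The 6.0 h medians come from 3 patients per cohort, without actual sampling times. This stands, and it is why the lower end of the range is near zero.
- **Small against the plan.** No hypothesis is tested. Even the 0.944 case would move an estimated ratio of 2.00 to 1.89, well inside the planned AUC interval of 1.48 to 2.70 in Table 7. This also stands.
- **The later bar does the data no harm.** True. Its cost is that it leaves the 2 to 3 h window as the only compliant option.
- **A later window could expose the next dose.** Acid suppression before dosing would act on the whole dose. This is a fair warning against letting use run close to the next dose, and is why permitted use should stop at 72 h.

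A reader might also infer that timing cannot be verified because only dates are kept. The documents do not support that as a fault. Section 6.9 requires indication and daily dose as well, and the CRF, which may hold a time field, is not among them. Section 5.3.4 says "Participants will be confined to the procedure room for the first 4 hours after dosing on Day 1", so staff could observe use in that hour. Nor should the 4-hour standardisation rule be read as contradicting Section 6.9: it covers lying down, "eating, and drinking beverages other than water during the first 4 hours after dosing", and does not mention medicines.

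**Conclusion.** The point holds as a minor design flaw. The rule points the wrong way: it permits acid reducers when absorption may be incomplete and forbids them when the dose is essentially absorbed. The plausible shift from one affected participant is a factor of 0.999 to 0.944 on a geometric mean ratio, or 0.2% to 19% of the planned AUC half-width, with the upper end unlikely. These figures assume a one-compartment model, medians from three fasted patients, one user among 12, and for the upper end a 50% loss that has no source in the documents. No corresponding figure is offered for Cmax.

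A reader might infer that the rule will bias the food-effect estimates, or that half or more of a dose's exposure would be lost. Neither follows: use may never occur, the interaction size is unknown, and with Tmax near 2 h almost nothing is left to affect. The reason to act is that the correction is cheap before the first dose.

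**What to change.** Replace the sentence on other acid reducers in Section 6.9 with:

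*H2 blockers and antacids may be used only from 24 to 72 hours after a dose (from 24 hours after dosing in Period 3); if one is medically needed earlier to treat an AE, give it, notify the sponsor and record the clock time.*

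The prohibition of proton pump inhibitors is unchanged. The 72 h limit coincides with the end of PK sampling. The sponsor should confirm the resulting gap of about 48 h before the next dose against the agent's duration of action.

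Any exclusion of affected data stays with the existing SAP Section 5.3.1 rule for PK estimates known to be biased, so the SAP needs no change.

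The cost is one protocol sentence. A participant with mild dyspepsia on the dosing day waits up to 24 h for an antacid unless it is medically needed, and the clear interval before the next dose is shorter than under the present rule.
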